2.1 Safety Analysis Set

Safety analyses will be conducted using the safety analysis set on a treatment-emergent basis. As such, the safety analysis set will include all subjects/eyes exposed to any study lenses evaluated in this study. For treatment-emergent safety analyses, subjects/eyes will be categorized under the actual study lens exposed in the corresponding lens sequence.

Adverse events occurring from the time of informed consent but prior to first exposure to study lenses will be summarized in subject listings.

Document: TDOC-0054605 Version: 1.0; CURRENT; Most-Recent; Effective

Status: Effective

2.2 Full Analysis Set

The full analysis set (FAS) is the set of all randomized subjects who are exposed to any study lenses evaluated in this study.

2.3 Per Protocol Analysis Set

The per protocol (PP) analysis set is a subset of FAS and excludes all data/subjects which have met any of the critical deviation or evaluability criteria identified in the Deviation and Evaluability Plan.

3 Subject Characteristics and Study Conduct Summaries

The following tables will be presented:

- Subject Disposition by Lens Sequence
- Analysis Sets by Lens
- Analysis Sets by Lens Sequence
- Subject Accounting by Lens Sequence
- Demographics Characteristics by Lens Sequence
- Baseline Characteristics by Lens Sequence

Demographics and subject accounting tables will be summarized on the safety, full, and PP analysis datasets. Baseline characteristics will be summarized on the full and PP analysis datasets.

In addition, the following subject listings will be provided:

- Listing of Subjects Excluded from Protocol Defined Analysis Sets
- Listing of Lens Sequence Assignment by Investigator
- Listing of Subjects Discontinued from Study

4 Effectiveness Analysis Strategy

This study defines 1 primary,				
endpoints. All effectiveness evaluations will use the FAS as the primary analysis set.				
Supportive analyses of the primary	effectiveness endpoints will be			
conducted using the PP Analysis Set only if the number of subjects excluded from the PP				
Analysis Set exceeds 5% of the FAS.				

Document: TDOC-0054605 Version: 1.0; CURRENT; Most-Recent; Effective

Status: Effective

For all planned inferential analyses, alternative models/methods may be considered if convergence cannot be achieved. Furthermore, if significant carryover effects are noted (confounded with sequence effect), results will be examined by period, ie, exposure time point, to ensure the overall conclusion is valid.

All data obtained in evaluable subjects/eyes will be included in the analysis. No imputation for missing values will be carried out for the effectiveness analyses.

A listing of selected effectiveness data will also be provided.

4.1 Effectiveness Endpoints

Primary Endpoint

The primary endpoint is the percent of AOHG toric lenses with axis orientation within ± 30 degrees from the 90° axis (ideal location), 10 min. after lens insertion. This percentage is calculated for the binary variable derived based on axis location of each lens as defined below:

Yes – if the absolute difference between the axis location and 90 is less than or equal to 30 (ie, lens located between the 60° and 120° axis inclusive); or

No – otherwise.

Document: TDOC-0054605 Version: 1.0; CURRENT; Most-Recent; Effective

Status: Effective

4.2 Effectiveness Hypotheses

Primary Effectiveness

No inferences will be made on the primary effectiveness endpoint; therefore no hypotheses are formulated.

4.3 Statistical Methods for Effectiveness Analyses

4.3.1 Primary Effectiveness Analyses

Frequency and percentage of lenses classified as 'Yes' will be provided for AOHG toric and AO toric, and two-sided 95% confidence intervals (CI) based on the exact binomial distribution will be calculated. The following SAS pseudocode will be used to obtain the confidence interval.

```
Alcon - Business Use Only Statistical Analysis Plan Effective Date: 11-Dec-2017
```

Document: TDOC-0054605 Version: 1.0; CURRENT; Most-Recent; Effective

Status: Effective

proc freq data=effdata order=data;
by trtpn;
tables response_outcome/binomial (exact);
run;

A threshold of 90% (as a minimum) has been established for this endpoint based on historical data. Therefore, percent of 'Yes' for AOHG toric lenses will be compared numerically to 90%.

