3 PROTOCOL SUMMARY

This is a prospective, randomized, bilateral crossover, double-masked, controlled study. The study population will include approximately 35 subjects in 1 US site, with a potential 2nd US site being added if necessary to meet the target enrollment. The study will consist of volunteer subjects with normal eyes (other than correction for refractive error) who are at least 18 years of age, are adapted wearers of soft contact lenses, and have at least 3 months of soft contact lens wearing experience.

Two pairs of toric contact lenses (AOHG toric and AO toric) will be evaluated during 1 office visit in this crossover study. Subjects will be randomly assigned in a 1:1 manner to either receive AOHG toric or AO toric lenses for use during Period 1 of the study. For Period 2, the contact lenses that were not allocated for use in Period 1 will then be assigned per the specified sequence group:

Sequence Group

- 1) AOHG toric → AO toric
- 2) AO toric → AOHG toric

Subjects will wear Pair 1 assigned study lenses bilaterally for approximately 30 min before crossing over into Pair 2 assigned study lenses bilaterally for approximately 30 min. There will be a 30 (+15) min washout period between removal of Pair 1 and insertion of Pair 2 study lenses.

The following assessments will be performed monocularly in the right and left eye for Pair 1 and Pair 2 lenses (see section 10 for details):

Axis orientation 10 min after lens insertion

Document: TDOC-0054499 Version: 1.0; CURRENT; Most-Recent; Effective

Status: Effective Page 12 of 54

Once Pair 2 lenses are removed, the study exit procedures will be performed for each subject.

Investigational	Device
product type	
Study type	Interventional
Investigational	Test Product: AOHG toric lenses
products	Control Product: AO toric lenses
Purpose and	The overall purpose of this non-dispense study is to evaluate the
rationale	rotational characteristics of the AOHG toric lens, by assessing lens orientation as the primary variable compared to the commercially
	available AO toric lens.
Objective(s)	 The primary effectiveness objective of this study is to evaluate the percentage of AOHG toric lenses that orient within ± 30 degrees from the 90° axis (ideal location), 10 min after lens insertion. The safety objective is to describe the safety profile of the investigational products through evaluation of adverse events (AEs), biomicroscopy findings, and device deficiencies.
Endpoint(s)	Primary Effectiveness

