8 STUDY POPULATION

The study population consists of adult male and female subjects (aged 18 and over) with non-diseased eyes, who require optical correction for astigmatism. It is aimed to enroll approximately 35 subjects in 1 US site, with a potential 2nd US site being added if necessary to meet target enrollment. Site-specific targets may vary based upon individual site capabilities. Estimated time needed to recruit subjects for the study is approximately 4 weeks.

The intended study population consists of volunteer subjects aged 18 or over who are adapted soft contact lens wearers, have at least 3 months of contact lens wearing experience, and who wear their habitual lenses at least 3 days per week and at least 8 hours per day.

Subjects must require contact lens sphere power from -0.50 to -8.00 D; cylinder power less than or equal to -2.25 DC; and for cylinder powers greater than -1.00 DC, axis should be between 60° to 120° or 30° to 150° inclusive. Because an approximately 10% screening failure rate is expected, approximately 35 subjects are expected to be enrolled to obtain a target of 30 completed subjects.

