10 STUDY PROCEDURES AND ASSESSMENTS

Subjects will be expected to attend only 1 office visit which includes 2 different study periods, 30 minutes each. Subjects will wear Pair 1 assigned study lenses bilaterally for approximately 30 min before crossing over into Pair 2 assigned study lenses bilaterally for approximately 30 min. There will be a 30 minute (+15 min) washout period between removal of Pair 1 and insertion of Pair 2 study lenses.

All study procedures and assessments will be conducted during the 1 office visit before subject is exited at the end of the single visit.

During Period 1, the study procedures will be conducted in the following order:

 Subjects will insert the first pair of lenses in the randomized sequence, being instructed to always begin with the right lens.

 The following assessments will then be performed monocularly in the right and left eye:

Document: TDOC-0054499 Version: 1.0; CURRENT; Most-Recent; Effective

Status: Effective Page 34 of 54

• Axis orientation 10 min after lens insertion.

The procedures described above will be repeated for the second pair of study lenses in the randomized sequence for Period 2.

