12.4.1 Analysis of Primary Effectiveness Endpoint(s)

The primary endpoint is the percent of AOHG toric with axis orientation within ± 30 degrees from the 90° axis (ideal location), 10 min after lens insertion. This percentage is calculated for the binary variable derived based on axis location of each lens, as defined below:

Yes – if the absolute difference between the axis location and 90 is less than or equal to 30 (ie, lens axis located between the 60° and 120° axis inclusive)

No – otherwise

Document: TDOC-0054499 Version: 1.0; CURRENT; Most-Recent; Effective

Status: Effective Page 46 of 54

[figure not shown]

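### The primary 95% CI treats about 60 paired lenses from 30 subjects as independent, so it is too narrow on average, and can cover less than 95%, if fellow eyes are positively correlated

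*SAP*

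**What the plan says.** The response is defined lens by lens. Protocol 12.4.1 states: "This percentage is calculated for the binary variable derived based on axis location of each lens", and SAP 4.1 repeats the definition. Both eyes contribute for each product. Protocol section 10 has it that "Subjects will wear Pair 1 assigned study lenses bilaterally for approximately 30 min before crossing over into Pair 2 assigned study lenses bilaterally", and the Protocol Summary adds: "The following assessments will be performed monocularly in the right and left eye for Pair 1 and Pair 2 lenses". Section 4 of the SAP brings in all data from evaluable eyes, and neither document has a one-eye rule. Protocol section 8 gives the number of people: "approximately 35 subjects are expected to be enrolled to obtain a target of 30 completed subjects".

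Protocol 12.4.1.2 asks only for a two-sided CI. SAP 4.3.1 makes it specific: "two-sided 95% confidence intervals (CI) based on the exact binomial distribution will be calculated". The code is PROC FREQ by treatment with the statement "tables response_outcome/binomial (exact", and no subject identifier appears in it.

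On use of the result, SAP 4.2 says: "No inferences will be made on the primary effectiveness endpoint; therefore no hypotheses are formulated". SAP 4.3.1 says that the percent of Yes "for AOHG toric lenses will be compared numerically to 90" percent. The precision statement (Protocol 12.8, SAP section 7) uses a sample size of 30.

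**The concern.** An exact binomial interval assumes independent trials. Two lenses of the same design, worn by one person at one sitting and assessed together, cannot be presumed independent: lid and corneal features that rotate one lens may well rotate the other. With positive correlation, 60 lenses carry less information than 60 independent observations, and the interval does not reflect this. The primary method and its code are visible in full, so redaction does not explain the omission.

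The stake is limited but real. No test is performed, and the 90% criterion looks only at the observed percentage. The interval is what a reader would use to judge how firmly the test lens clears 90%. It is labelled 95%, and no other measure of uncertainty is planned for that percentage.

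**Working it through.** **Inputs.** 30 completers (Protocol section 8). Two lenses per subject per product (Protocol sections 3 and 10). Exact two-sided 95% interval (SAP 4.3.1). Expected proportion 0.90 with n = 30 (Protocol 12.8, SAP section 7). The ICC between fellow eyes is not given, so 0 to 1 is assumed.

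**1. The plan's own precision figure.** The normal-approximation half-width is 1.96 × √(0.90 × 0.10 / 30) = 0.107, which agrees with the stated value of about 0.10. It counts subjects. With 60 independent lenses it would be 1.96 × √(0.09 / 60) = 0.076. The exact intervals are 73.5% to 97.9% for 27/30 and 79.5% to 96.2% for 54/60. Sizing therefore takes no credit for the second eye, but the reported interval does.

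**2. Coverage of the planned interval.** Let p be the true rate and q = 1 − p. For one subject:
- P(both Yes) = p² + ICC·pq
- P(one Yes) = 2pq(1 − ICC)
- P(both No) = q² + ICC·pq

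Full enumeration over 30 subjects, at p = 0.90:

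| ICC | Coverage of planned 95% CI |
|---|---|
| 0 | 97.2% |
| 0.2 | 95.5% |
| 0.3 | 94.5% |
| 0.5 | 92.5% |
| 0.7 | 90.5% |
| 1 | 88.4% |

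The ICC above which coverage is below 95% depends on the true rate, and not monotonically:

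| True rate | ICC at which coverage reaches 95% |
|---|---|
| 85%, 90% | 0.25 |
| 91% | 0.08 |
| 92% | 0.29 |
| 93% | 0.15 |
| 94% | 0.18 |
| 95% | about 0.92 |
| 97% | about 0.91 |
| 96%, 98% | never |

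**3. The same data with the subject as cluster.** Let xᵢ be the number of Yes lenses (0, 1 or 2) in subject i.
- Clustered variance: V = (30/29) · Σ(xᵢ − 2p̂)² / 60²
- Effective n = [p̂(1 − p̂)/V] × (t₅₉/t₂₉)², capped at 60, where (2.001/2.045)² = 0.957
- The interval is Clopper-Pearson at that effective n.

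Example: 54/60 Yes with three subjects missing in both eyes. The sum is 27 × 0.2² + 3 × 1.8² = 10.8. V = (30/29) × 10.8/3600 = 0.00310. Then 0.09/0.00310 = 29.0, and 29.0 × 0.957 = 27.8.

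| Subjects missing in both eyes (54/60 Yes) | Σ(xᵢ − 2p̂)² | Effective n | Clustered CI | Planned CI |
|---|---|---|---|---|
| 0 | 4.8 | 60 (capped) | 79.5–96.2% | 79.5–96.2% |
| 1 | 6.8 | 44.1 | 77.2–97.0% | 79.5–96.2% |
| 2 | 8.8 | 34.1 | 74.8–97.6% | 79.5–96.2% |
| 3 | 10.8 | 27.8 | 72.6–98.1% | 79.5–96.2% |

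**4. Expected width at p = 0.90.**

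| ICC | Planned | Clustered |
|---|---|---|
| 0 | 0.164 | 0.172 |
| 0.2 | 0.163 | 0.186 |
| 0.5 | 0.162 | 0.208 |
| 1 | 0.160 | 0.246 |

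**5. All lenses Yes.** The ICC cannot then be estimated. The exact lower limit is 0.025^(1/60) = 94.0% counting lenses and 0.025^(1/30) = 88.4% counting subjects. The clustered lower limit for 59/60 is 90.7%, so the subject count alone would rank a perfect result below a near-perfect one. Over 120 scenarios (true rate 85% and 90% to 98%, ICC 0 to 1), minimum coverage of the clustered interval is 95.5% with the subject-count limit for all-Yes results. With the lens-count limit it is 83.6% (true rate 94%, ICC 1), where the planned interval covers 81.2%. The widths in step 4 use the subject-count limit; at p = 0.90 the other limit changes them by at most 0.003.

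**The case against.** The strongest reply is that nothing turns on this interval. The endpoint is descriptive, the criterion uses the point estimate, and the sizing counts subjects. That is correct and caps the importance of the point, but it does not make a mislabelled 95% interval acceptable.

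The shortfall also rests on an unknown ICC, and the exact method has some slack. At a true rate of 90% it holds its level up to an ICC of 0.25. At 95% or above it fails only near complete correlation, or not at all. Since 90% is set as a minimum, such rates are plausible. This stands, so the claim is that coverage can fall below 95%, not that it will.

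Nor is the planned interval narrower in every dataset: with 54/60 and no bilateral misses the two are identical. The statement holds on average and like for like. A Wald-type clustered interval at 90% observed would be wider than the planned one only above an ICC of about 0.22.

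Finally, the remedy costs width where coverage is already adequate. At a true rate of 95% and ICC 0.5, the planned interval covers 97.1% with expected width 0.123; the clustered one covers 98.9% with width 0.161, about 31% wider. It also gives two limits, not one, when every lens is Yes. Both are fair costs. The reason to accept them is that the planned interval gives the same answer whether six misses come from six subjects or from three.

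**Conclusion.** The concern holds. The primary interval assumes independent fellow eyes, and no visible primary-analysis text supports or corrects that assumption. At a true rate of 90%, coverage is 94.5% at ICC 0.3, 92.5% at 0.5 and 88.4% at 1. For an observed 54/60, the lower limit is overstated by up to 6.9 percentage points (79.5% against 72.6%). These sizes rest on 30 complete pairs, exchangeable eyes and an assumed ICC. The observed percentage, the numerical comparison with 90% and the sample size do not change. It should be fixed because it concerns the stated precision of the primary result; it does not undermine the decision rule.

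**What to change.** Keep the lens percentage and the numerical comparison. In SAP 4.3.1, replace the interval for each product with one that takes the subject as the cluster. One option is Clopper-Pearson on the effective sample size with the t adjustment, capped at the number of lenses, as in PROC SURVEYFREQ with a CLUSTER statement for subject, requested for the Yes level. State in advance that if all lenses are Yes, both exact lower limits will be shown as bounds (94.0% for 60 lenses, 88.4% for 30 subjects), with neither presented alone.

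The cost is SAP wording and a few lines of code; no new data are needed. The interval is usually somewhat wider. With no correlation and a true rate of 90%, expected width rises from 0.164 to 0.172; at higher true rates the relative widening can be larger, as noted above. With three bilateral misses in 54/60, the t adjustment makes it slightly wider (72.6% to 98.1%) than the exact interval for 27/30 subjects (73.5% to 97.9%).

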5.2 Purpose of the Study

The overall purpose of this non-dispense study is to evaluate the rotational characteristics of the AOHG toric lens, by assessing lens orientation as the primary variable and comparing it to the commercially available AO toric lens.

At the end of the study, a clinical study report will be prepared in accordance with applicable regulatory requirements and standards.

There are no immediate plans to submit the results of this development study for publication; however, the results may be offered for publication if they are of scientific interest, or if the results relate to a product that is subsequently approved or cleared for marketing.

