Document: TDOC-0054605 Version: 1.0; CURRENT; Most-Recent; Effective

Status: Effective

Short Title:

Statistical Analysis Plan CLC127-C001 / NCT03392532

Full Title:

Statistical Analysis Plan CLC127-C001

Protocol Title: Axis Orientation Comparison of Two Silicone Hydrogel Toric

Contact Lenses

Project Number: A02946

Protocol TDOC Number: TDOC-0054499

Author: , MS

Template Version: Version 1.0

Approvals: See last page for electronic approvals

Job Notes:

This is the original (Version 1.0) Statistical Analysis Plan for this study. This version of the Statistical Analysis Plan is based on Version 1.0 of the study protocol.

Document: TDOC-0054605 Version: 1.0; CURRENT; Most-Recent; Effective

Status: Effective

Executive Summary:

Key Objective:

To evaluate the percentage of AIR OPTIX plus HydraGlyde for Astigmatism soft contact lenses (AOHG toric) that orient within \pm 30 degrees from the 90° axis (ideal location), 10 min after lens insertion.

Decision Criteria:

A threshold value of 90% (as a minimum) for the percentage of lenses orienting within ± 30 degrees of the 90° axis has been established for AOHG toric, based on historical data.

${\bf Alcon \textbf{-} Business} \ Use \ Only \ {\tt Statistical} \ {\tt Analysis} \ {\tt Plan}$

Document: TDOC-0054605 Version: 1.0; CURRENT; Most-Recent; Effective

Effective Date: 11-Dec-2017

Status: Effective

Table of Contents

Statistic	cal Analysis Plan CLC127-C001	1
Table of	f Contents	3
List of T	Tables	4
List of I	Figures	4
1	Study Objectives and Design	5
1.1	Study Objectives	
1.2	Study Description	
1.3	Randomization	
1.4	Masking	6
1.5	Interim Analysis	6
2	Analysis Sets	6
2.1	Safety Analysis Set	6
2.2	Full Analysis Set	7
2.3	Per Protocol Analysis Set	7
3	Subject Characteristics and Study Conduct Summaries	7
4	Effectiveness Analysis Strategy	7
4.1	Effectiveness Endpoints	8
4.2	Effectiveness Hypotheses	9
4.3	Statistical Methods for Effectiveness Analyses	9
4.3.1	Primary Effectiveness Analyses	9
4.4	Multiplicity Strategy	
4.5	Subgroup Analyses and Effect of Baseline Factors	
4.6	Interim Analysis for Effectiveness	11
5	Safety Analysis Strategy	11
5.1	Safety Endpoints	11
5.2	Safety Hypotheses	11
5.3	Statistical Methods for Safety Analyses	11
5.3.1	Adverse Events	12
5.3.2	Biomicroscopy Findings	12

Alcon - Bu	siness Use Only Statistical Analysis Plan	Effective Date: 11-Dec-2017
Document: T	Version: 1.0; CURRENT; Most-Recent;	Effective
Status: Effe	ctive	
5.3.3	Device Deficiencies	13

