1.1 Study Objectives

PRIMARY OBJECTIVE

To evaluate the percentage of AOHG toric lenses that orient within \pm 30 degrees from the 90° axis (ideal location), 10 min after lens insertion.

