4.4 Multiplicity Strategy

Since only one endpoint will be tested inferentially, there is no concern for multiplicity.

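### Should the ±30° primary analysis give a paired AOHG minus AO difference with an interval?

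*SAP*

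**What the plan says.** The SAP's title page gives the protocol title as "Axis Orientation Comparison of Two Silicone Hydrogel Toric" contact lenses. Protocol 5.2 describes the overall purpose as evaluating rotation "by assessing lens orientation as the primary variable and comparing it to the commercially available AO toric lens"; the Protocol 3 summary says much the same. Each subject wears both lens pairs in randomised order, and orientation is read in both eyes in each period.

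The primary objective is narrower. SAP 1.1 states it as "To evaluate the percentage of AOHG toric lenses that orient within" ±30° of the ideal axis, 10 minutes after insertion, and Protocol 6.1 agrees. In SAP 4.3.1, "Frequency and percentage of lenses classified as 'Yes' will be provided for AOHG toric and AO toric", with separate two-sided exact 95% intervals (the code runs by treatment). The same section adds that the Yes percentage for "AOHG toric lenses will be compared numerically to 90"%. Protocol 12.4.1.1 and SAP 4.2 rule out any inference on this endpoint.

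**The concern.** A crossover in which the same eyes wear both lenses normally calls for a within-subject contrast, and the title and purpose seem to promise one. The visible primary analysis gives two one-sample summaries. A reader can subtract the percentages but cannot work out the precision of the difference. That precision depends on how many eyes are Yes on one lens and No on the other, and no planned table shows this.

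If AOHG landed on 90% and AO a few points higher, the report would show the gap without its uncertainty. The gap could then be over-read or dismissed.

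**Working it through.** **The plan's own precision figure.** Protocol 12.8 and SAP 7 state that a 95% interval extends about 0.10 when the proportion is 0.90 and n = 30. Check: 1.96 × √(0.90 × 0.10 / 30) = 0.107, which agrees. It is a single-proportion figure, as one would expect for an endpoint that is not a between-lens contrast.

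**The comparator named for this endpoint.**
- Objective (Protocol 6.1, SAP 1.1): AOHG percentage only.
- Endpoint (Protocol 12.4.1, SAP 4.1): AOHG percentage only.
- Decision criterion (SAP Executive Summary): at least 90% for AOHG.
- Analysis table in Protocol 3: the comparison column gives the 90% threshold, and the method is descriptive.
- Analysis (Protocol 12.4.1.2, SAP 4.3.1): AOHG against 90%, with AO's percentage and interval reported alongside.

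These agree with one another. The title and purpose describe the whole study and orientation in general. They do not say that the ±30° dichotomy must carry the contrast with AO.

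**Signs of a comparison in the removed text.**
- SAP 4.4: "Since only one endpoint will be tested inferentially, there is no concern for multiplicity". That endpoint cannot be the primary one, since inference on the primary is ruled out.
- SAP 4, on planned inferential analyses, allows for models that fail to converge and examines results by period "if significant carryover effects are noted". Neither provision is needed for a one-sample percentage; both suit a between-lens crossover model.
- Protocol 6 goes from 6.2 to 6.4, and the entry for Table 6–2 is blank.
- The Protocol 3 data analysis text speaks of endpoints, in the plural, collected at 10 minutes. The visible 10-minute assessment is axis orientation.

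This does not prove that the tested endpoint compares orientation between lenses. It does mean that the lack of such a comparison cannot be asserted.

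**What the paired interval would add.** Illustrative inputs: 30 subjects, 60 eyes per lens, AOHG 54 Yes (6 No), AO 57 Yes (3 No). The difference is (54 − 57)/60 = −5.0 points. If k eyes are No on both lenses (k = 0 to 3), discordant eyes number 6 + 3 − 2k = 9, 7, 5 or 3.

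Take each subject's difference as the mean over two eyes, so that one discordant eye contributes ±0.5. Then SS = Σd² − 30 × 0.05², and the half-width is 2.045 × √(SS / (29 × 30)), ignoring sequence.

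| Discordant eyes | Σd² | SS | Half-width | 95% interval (points) |
|---|---|---|---|---|
| 3 | 0.75 | 0.675 | 0.057 | −10.7 to +0.7 |
| 5 | 1.25 | 1.175 | 0.075 | −12.5 to +2.5 |
| 7 | 1.75 | 1.675 | 0.090 | −14.0 to +4.0 |
| 9 | 2.25 | 2.175 | 0.102 | −15.2 to +5.2 |
| 9, clustered* | 4.25 | 4.175 | 0.142 | −19.2 to +9.2 |

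*Three subjects at −1, one at +1, one at +0.5; in the other rows the discordant eyes fall in different subjects.

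The planned exact intervals are the same in every row: 79.5% to 96.2% for AOHG and 86.1% to 99.0% for AO. So the pairing does matter for the width. But every row includes zero, and AOHG's 90.0% meets the threshold in all of them.

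**Expected precision.** With 90% Yes on both lenses and 28 df, the half-width is 2.048 × √[2 × 0.09 × (1 − φ) × (1 + r) / 2 / 30]. Here φ is the between-lens correlation and r the between-eye correlation of the differences. The documents give neither, so both are assumed:
- φ = 0.7, r = 0: 0.061
- φ = 0, r = 0: 0.112
- φ = 0, r = 1: 0.159

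The estimate would therefore carry roughly ±6 to ±16 points.

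**The case for a change.** The best case for the concern is that the paired data will exist, a descriptive interval needs no hypothesis, and the plan already gives intervals for this endpoint. All of that is true. It is also true that the two separate intervals cannot yield the precision of the difference. SAP 4 plans a listing of selected effectiveness data, but its contents are not stated, so it cannot be relied on to fill the gap.

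A sharper example has AOHG at 54/60 and AO at 60/60. The paired difference is −10.0 points, with a Tango score interval of −20.1 to −3.4 if the 60 pairs are treated as independent. The separate intervals (79.5% to 96.2% and 94.0% to 100%) overlap. This stands as arithmetic. But with no failures on AO, all six AOHG failures must be discordant, so that count can be read from the planned percentages; only the clustering within subjects stays hidden. The 90% comparison is again unaffected.

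It is also argued that AO is the in-study yardstick for the 90% figure. The documents do not say so. They attribute the threshold to historical data without tying it to AO, and Protocol 7.4 says only that AO was chosen to address the study objectives.

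**Conclusion.** The concern does not hold. For the ±30° endpoint, the objective, definition, named comparator, decision criterion and analysis all agree, and AO's result is shown next to AOHG's. A paired difference would change neither the planned percentages nor the 90% decision. In the main worked case its interval includes zero under every pairing shown, and its expected half-width is about 6 to 16 points under assumed correlations. Asking for it is a preference for one more descriptive line.

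This rests on two things. The primary endpoint is meant to be judged against a threshold, which the documents state consistently. And removed text is not counted as missing: the visible wording shows that a further, inferentially tested endpoint exists, though not what it measures. If the full documents turned out to hold no between-lens analysis of orientation, the fit between the stated purpose and the analyses would deserve another look. The public text does not support that conclusion.
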